### **Female VHA patients: Eligibility, recruitment, and procedures**

Inclusion criteria are the same as the criteria that we have successfully adopted for Phase 2 of the study. Specifically, female VHA patients (n=60-68) who meet the following inclusion criteria will be eligible to participate: (1) have experienced past-year IPV; (2) willingness to participate in pre-treatment, post-treatment and follow-up assessments (including questionnaires and post-treatment interviews), as well as to be randomly assigned to an intervention condition; (3) not at acute risk of suicide or homicide requiring hospitalization; (4) not demonstrating symptoms of mania, psychosis, or intoxication at the time of screening or sessions; (5) capacity to consent to study; (6) willingness to have the intervention session(s) audio recorded. Prior participation in the RISE open trial as part of Aim 2 will be an additional exclusion criteria, and during the COVID-19 pandemic while enrollment is solely virtual due to restrictions on face-to-face appointments, inability/unwillingness to do the enrollment session virtually so researchers can obtain a screenshot of the ICF, receive materials by mail, and/or provide personal email (i.e., to receive VVC appointment information, intervention materials) are additional exclusion criteria.

**Recruitment Letter Considerations:**

Our Co-I, [name], has conducted recent HSR&D-funded research at the Philadelphia VAMC and Portland VAMC to enlist women VA patients who have experienced past-year IPV. She has developed safe and effective recruitment methods for recruiting that she has used in this work that we would like to apply for our study. She has presented these recruitment methods on two national VA Cyber Seminars on recruiting women to participate in research (see her Power Point presentation attached). For their IPV study, they sent letters to women who had visits at the respective study sites within the past-year. These letters included vague language about a study to understand women's interpersonal relationships and healthcare needs, direct mention of financial compensation, and invited women to "opt out" of being contacted. This strategy, although time consuming for the research team, was effective in securing their desired sample size of 160+ women who experienced past-year IPV. Of note, only 3.2% of the women who received letters opted out of being contacted. Of those who were reached by phone, there were only two women across the two study sites who indicated that they did not like being contacted for research by VA (but it was not specific to it being about IPV). It is notable that not one single woman expressed concerns to the interview team about being contacted via letters or phone using the opt-out method. We understand that VA Boston has been moving away from opt out strategies. However, we believe this method is highly appropriate for our study.

To balance concerns of IRB and what is effectively done in other related research, we propose to recruit via patient letters by contacting potential participants included on a patient list generated from the electronic medical records/CPRS (i.e., Corporate Data Warehouse), which will be saved in a password protected file in a secure drive behind the VA firewall. Potential participants on this list include women ages 18-55 who have had a primary care or mental health appointment at VA Boston within the past year. This letter is purposefully generic to protect the privacy and safety of women who receive the letter. The letter includes information about the voluntary nature of the study and the option to "opt out" from further contact by notifying us by phone or pre-stamped letter and self-addressed envelope. Women who do not opt out within 10 days of the letter being sent will be contacted. Women may contact us directly to learn more about the study and determine if they are eligible to participate. Our phone screen script includes necessary elements of consent and confirmation that women are in a private, safe space where they can speak before moving forward with the phone screening (please see phone screen script attached to this amendment). We will temporarily discontinue recruiting via letters during the COVID-19 pandemic and will plan to resume this previously approved recruitment strategy after stay at home orders are lifted and the study team returns to the VA Boston medical center.

To augment these recruitment efforts, we will also recruit via flyers and brochures advertising the study opportunity in strategic locations within VA, including the Women's Health Center and other key locations (e.g., mental health clinics, HUD-VASH, etc.). A previously approved submission included flyers and handouts, which contain information about the purpose of the study and phone number for learning more about the study. Interested women will have the option of meeting with study staff to learn more about the study and participate in eligibility screening. Women may also schedule a phone screening at a time that is convenient and safe for them.

Upon contact with research staff, interested women will participate in a brief screening interview to determine eligibility (by phone for those who call and in-person for others), after which a member of the research team (PI, PM or RA) will examine patient's electronic medical record to ensure that she does not meet exclusionary criteria (see attached list of exclusionary criteria to be examined in CPRS; any questionable criteria will be reviewed by PI and/or PM to determine eligibility). As per approved Phone Screening Script for Phase 3, study staff obtain verbal consent during the phone screening to mail a letter if the participant is unable to be reached by phone (please see patient letter in appendix). Ineligible women and those who decline

participation will be offered information on relevant resources within VA and the community (e.g., Passageway Program at Brigham and Women's Hospital, National DV Hotline, etc.). Patients who meet inclusion criteria will be scheduled based on participant and provider availability as soon as possible, ideally within two weeks. At this visit they will fully review and sign informed consent documents and HIPAA Authorization (see Informed Consent document and HIPAA forms attached). Because women will be asked to complete questionnaires that include demographics information about themselves and IPV exposure, participants will complete the HIPAA authorization form. Patients will complete the pre-treatment assessment questionnaires (described below), after which patients will receive their randomly assigned 60-minute intervention session (RISE or information/referral, which is referred to as the "Make the Connection" intervention in the informed consent form). In some cases (particularly during the COVID-19 pandemic, given the requirement to not hold face to face meetings), informed consent will be conducted remotely rather than face to face appointment. In those situations, study staff will speak with potential study participants during the phone screening prior to their informed consent/enrollment appointment to ensure that it is safe for participants to receive study materials in the mail, after which two copies of the informed consent (one for the study team, one for the participant to keep) will be mailed to the participant along with an addressed stamped envelope. During the phone screening, study staff will also confirm that it is safe for participants to receive emails, which will be used for telehealth appointments and the distribution of study materials. A videoconference session using VA-approved platforms (e.g., VVC) will be scheduled with the participant, during which the study team member reviews the ICF with the participant. If the participant agrees to sign the ICF, they will hold up the signed ICF page to the computer camera so the study team member can take a screen shot of the signed ICF. The screen shot will be saved directly to our secure project folder (in a file separate from any other data collection) as documentation of the signed ICF. The participant will be asked to mail the signed ICF back to the study team using the provided pre-stamped addressed envelope. If the original signed ICF is received, it will be saved along with the printed screen shot picture of the signed ICF.

#### **Randomization and intervention delivery.**

Patients (women veterans) will be randomized within site to condition. Randomizing providers to only one condition risks that RISE delivery skill may be imbalanced across conditions. We recognize that when providers are involved in both conditions, provider learning may blend into both conditions (e.g., use of motivational interviewing (MI) skills for selecting RISE modules influencing information/referral delivery). We anticipate the risk of the latter is limited because the RISE materials explicitly prompt MI strategies whereas the comparison condition does not. Thus, providers will deliver both interventions. This will also allow providers to contrast RISE with a more minimal intervention when providing perspectives on feasibility and acceptability. We will record all sessions in both conditions and we will assess and monitor condition fidelity and treatment differentiation using adherence checklists that contain the critical RISE and the information/referral elements. We will use software to conduct a simple randomization process to assign women to an intervention condition. The individuals conducting the informed consent will not be aware of the participants assigned condition until the participant has completed the signed informed consent and HIPAA Waiver (assignment of condition will be in a sealed envelope). Although we had considered using stratified randomization to balance conditions on patient characteristics (e.g., age, IPV frequency), there is no a priori reason to expect such factors to significantly influence our primary outcomes, although we will include demographic/relationship factors as covariates in our analyses if demographic/relationship characteristics differ across groups (see Quantitative Data Analysis Plan below). During COVID-19, following the participant's consent, the study team will email intervention materials to the participant for use during their same day intervention session.

**Information/referral intervention.** The information/referral condition is referred to as the "Make the Connection" intervention in the informed consent form. The title of this intervention reflects some of the underlying purpose of the information/referral condition, which is to make the connection between IPV and

health, and finding out how to connect with resources that may be of use. Provision of education about IPV and resource information is considered the “standard of care” within VHA (and the community). Participation in this information/referral intervention consists of a one-time 60 minute brochure-based educational session. In this session, providers will walk through an IPV educational brochure with the participant (see attachment). This brochure was developed by Drs. [name] and [name] to guide clinician responses to IPV disclosures within VHA. Using the brochure as a guide, the providers will provide tailored psychoeducation and discussions about: (1) the different forms of IPV (i.e. physical, sexual, psychological, etc.); (2) the effects of IPV on physical, mental, and social health; (3) discussion of safety planning; and (4) local and national IPV-related resources. Supportive statements and validation will be provided throughout (i.e., IPV is not your fault; I’m sorry this is happening to you). The provider will inquire about potential VHA referrals that may be of interest to the woman, and place consults/make referrals as requested. Similarly, the provider will offer to make phone calls with the participant to any of the community resources that she may be interested in learning more about. The intervention will conclude ensuring the woman has the National Domestic Violence Hotline, and offer a discreet ‘wallet card’ for women who desire to take that information with them. They will be informed they will be contacted by phone to schedule their post-treatment assessments. Intervention sessions will occur in private office space within primary care and/or mental health (e.g., Women’s Division of the National Center for PTSD) or within a private location within the providers’ home during the COVID-19 crisis.

**RISE.** The RISE will be delivered as per the refined manual, with its variable-length format (1 to up to 6 sessions within an approximate 10 week period). Following completion of the initial 60-minute RISE session, the provider and participant will determine whether they will have an additional session, and if so, it will be scheduled. Because RISE is specifically designed to be variable-length and patient-centered, it is possible that a participant may only desire to have 1 RISE session. Based on patient and provider feedback during Phase 2, all 6 of the RISE sessions can be up to 60 minutes. Originally, the subsequent sessions were intended to be 30-40 minutes, but that has proved infeasible. Both patients and providers have suggested that more time is allotted for subsequent sessions. Participants may have up to 6 RISE sessions in total. Intervention sessions will occur in private office space within primary care and/or mental health (e.g., Women’s Division of the National Center for PTSD). During times of unforeseen circumstances, such as the COVID-19 public health crisis of 2020, the clinical research sessions will be offered in telehealth format from the homes of licensed clinical psychologists [name] and [name], ensuring safe and private conditions for both the interventionists and the participants by following VA Boston’s and national VVC guidance for such clinical care. Individuals in the RISE condition will also complete the four brief validated self-report measures of empowerment, self-efficacy, patient activation, and valued action at the beginning of each RISE session to gauge treatment progress in real time and guide module selection, as we have done in Phase 2. Note these measures will be collected by the interventionist over the phone for any telehealth visits. This process takes approximately 10 minutes (leaving approximately 50 minutes for the RISE session). Participants will initially be emailed RISE intervention materials following their consenting/enrollment session, after which they will have the option to receive RISE intervention materials via USPS mail.

**Female VHA Patient Assessments.** Data collection takes place throughout the study and is modeled after a prototypical Hybrid 1 trial . We will administer a full battery of psychosocial assessment at pre-treatment, post-treatment assessment (i.e., 10-weeks post enrollment), and 1 month follow-up (i.e., 14 weeks post-enrollment) described below under “Measures.” Participants in the RISE condition will also complete four brief measures of empowerment, self-efficacy, patient activation and valued action at the beginning of each RISE session. At the posttreatment and follow-up assessment, patients will complete a brief audio-recorded semi-structured interview about their experiences with their respective intervention. The post-treatment and follow-up assessments will either be conducted by phone or in person, depending on the participant’s preference (thus allowing for them to determine what is most safe and preferable for them). Women will be compensated with

\$25 for completing the pre-treatment assessment. Upon completion of the post-treatment assessment, women will receive \$50 in cash or by check for their time and participation. Upon completion of the follow-up assessment, women will receive a \$75 in cash or by check for their time and participation. A timeline of all measures is available below in Table 4.

Table 4. Timeline of Assessments	Pre	10-week	14-week
Demographics (age, race, sexual orientation, # deployments)	X		
Demographics (relationship status, housing status)	X	X	X
Personal Progress Scale	X	X	X
Patient Activation Measure- Short Form (PAM-13)	X	X	X
Valued Living Questionnaire (VLQ)	X	X	X
Center for Epidemiological Studies- Depression Scale (CES-D)	X	X	X
Health Service Use	X	X	X
The Conflict Tactics Scale-Revised (CTS-2)	X	X	X
PTSD Checklist for DSM-5 (PCL-5)	X	X	X
Patient Health Questionnaire- 15 (PHQ-15)	X	X	X
12-item Short Form Survey (SF-12)	X	X	X
Safety Behaviors Checklist (SBC)	X	X	X
Connor-Davidson Resilience Scale (CD-RISC 25)	X	X	X
Client Satisfaction Questionnaire 8 (CSQ-8)	X	X	X
Depression Anxiety Stress Scale- (DASS)	X	X	X
Coping Strategy Inventory-Short Form (CSI-SF)	X	X	X
Acceptability		X	X
IPV-Related Head Injury	X		

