### **Measures**

#### **For Women VA Patient Participants:**

Demographics: A brief measure of background information (e.g., age, race, sexual orientation, relationship status, number of deployments, housing status). Background information surrounding age, race, sexual orientation, and number of deployments will be collected at Pre, while demographic information on relationship status and housing status will be collected at all three timepoints (table 4).

Personal Progress Scale – Revised: A measure of empowerment in women, demonstrating excellent reliability and validity in diverse sample of women.

General Self-efficacy Scale (GSS)65a: A reliable and valid 10-item scale that is designed to assess optimistic self-beliefs to cope with a variety of difficult demands in life.

Patient Activation Measure-Short Form (PAM-13)65b: A brief validated measure of patient activation including: patient knowledge, skill, and confidence for self-management. The 13-item abbreviated measure has psychometric properties similar to the original 22-item version.

Valued Living Questionnaire (VLQ): The VLQ is a two-part questionnaire that measures (a) the importance of 10 valued areas of living, and (b) the extent to which one's actions are consistent with one's values. For each domain (e.g., family, physical self-care, friends/social life), respondents use a 1–10 scale to rate how important each value is to them and how consistently they have lived in accordance with this value over the past week. Responses from both importance and consistency are multiplied to derive a value composite score.

Center for Epidemiologic Studies – Depression Scale (CES-D): The CES-D is a psychometrically sound and widely-used 20-item questionnaire designed to measure the frequency of past-week depressive symptoms. It is sensitive to change over relatively short periods of time.

Health Service Use (HSU): Assesses VA and non-VA health service use using a modified version of [name] health service use (HSU) measure. This measure has been used in prior studies by [name] (HSR&D IIR 12-345) and has been modified slightly for the purposes of this study. This will allow us to examine whether RISE leads to increased access and engagement with relevant health services.

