### Quantitative Data Analyses (Aim 3)

We will conduct multilevel longitudinal data analyses to examine change in psychosocial outcomes. Time will be coded as 0, 1, and 2 respectively for pretreatment, posttreatment, and 1-month follow-up; therefore, the Level-1 intercept will represent initial status and the Level-2 time coefficient will represent change over time. We will also evaluate a model using linear and quadratic polynomial contrasts and orthogonal contrasts to evaluate non-linear (i.e., non-constant) change. We will add a dummy-coded intervention variable (RISE vs. information/referral condition) as a predictor of the Level-1 change parameters (initial status and change over time) to evaluate the treatment x time interaction (i.e., does group membership moderate change in the outcomes?). This analytic strategy will produce effective and efficient tests of change in outcomes, even in the presence of attrition, and provides us with flexibility to assess and adjust for control variables, if needed (e.g., age, IPV frequency). We will calculate effect size estimates and 95% confidence intervals, which produce an estimate of  $d$  from multilevel analyses that is comparable to  $d$ 's produced using traditional methods (e.g., repeated measures ANOVA). To examine the range of effect sizes that might be reasonable to expect in a future trial, we will calculate effect sizes and 95% confidence intervals for all of our primary and secondary outcomes.

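### The planned treatment x time test is valid but loses precision by estimating a pre-treatment arm difference, and the covariate rule adds nothing to make up for it

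*Combined protocol and SAP*

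**What the plan says.** The model is in Quantitative Data Analyses (Aim 3). The pre-treatment score is a response, not a covariate: "Time will be coded as 0, 1, and 2 respectively for pretreatment, posttreatment, and 1-month follow-up". Arm then enters "as a predictor of the Level-1 change parameters (initial status and change over time) to evaluate the treatment x time interaction", so the arms may differ freely at time 0.

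Two statements govern other covariates. Under Randomization and intervention delivery, "we will include demographic/relationship factors as covariates in our analyses if demographic/relationship characteristics differ across groups". The analysis section adds only that the method gives "flexibility to assess and adjust for control variables, if needed (e.g., age, IPV frequency"). Neither defines a difference or a need, names a closed list, or says how a covariate would enter. The randomisation paragraph also says that "there is no a priori reason to expect such factors to significantly influence our primary outcomes".

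Allocation is by simple randomisation. The outcome scores needed for adjustment are already planned, under Female VHA Patient Assessments: "We will administer a full battery of psychosocial assessment at pre-treatment".

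**The concern.** Under simple randomisation a pre-treatment difference between arms is chance. A model that estimates it pays for a quantity known to be zero on average, and the treatment x time contrast behaves like a change score. In a trial of 60 to 68 women the wider standard error matters, because the score that would narrow it is already collected.

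The covariate rule does not recover that loss. It selects factors because they happen to be imbalanced, not because they predict outcome, from a set the plan expects not to be prognostic. It also leaves open which model is primary until the arms have been compared.

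**Working it through.** **Inputs.** From Quantitative Data Analyses (Aim 3): d=.5, f²=.15, PV=.1, 118 df, power .95. From the Aim 3 method text: 60 women analysed, up to 68 enrolled, 15% loss. From Measures: six demographic examples ("age, race, sexual orientation, relationship status, number of deployments, housing status"). Assumed because not stated: two-sided alpha .05, 1:1 allocation, equal SD of 1 at each visit, equal within-person correlation ρ between visits, ρ from .3 to .7.

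**1. The plan's own power.** Noncentral F with 1 and 118 df, λ = f² × 120.
- PV=.1: f² = .1/.9 = .111, λ = 13.3, power .952. This reproduces .95.
- d=.5: f² = d²/4 = .0625, λ = 7.5, power .775.
- f²=.15: λ = 18, power .988.

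The three stated effect sizes are not equivalent: with d = 2√f², PV=.1 is d=.67 and f²=.15 is d=.77. The calculation uses no within-person correlation, so it cannot show the effect of the baseline term.

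**2. Same final-visit contrast, two treatments of baseline** (n=30 per arm, d=.5, complete data).
- Change from pre-treatment: SE = √(2(1−ρ)) × √(2/30), 58 df.
- Adjusted for pre-treatment: SE = √(1−ρ²) × √(2/30), 57 df.
- SE ratio = √((1+ρ)/2).

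| ρ | SE change | SE adjusted | ratio | power change | power adjusted |
|---|---|---|---|---|---|
| .3 | .306 | .246 | .806 | .363 | .514 |
| .5 | .258 | .224 | .866 | .478 | .594 |
| .7 | .200 | .184 | .922 | .691 | .760 |

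The SE falls by 19%, 13% and 8%. A simulation of the adjusted analysis (20,000 trials) gave .507, .593 and .751, with type I error .047 to .050.

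**3. The planned three-wave linear test.** With times 0, 1, 2 and equal correlations, the within-person slope is (y2−y0)/2, so the free-baseline test is a change-score test. Generalised least squares, N=60, 118 df: power .37/.48/.70 with the arms free at baseline, .55/.62/.77 with them constrained equal. With categorical time, a random intercept and 15% missing the last visit (2,000 simulated trials), the final-visit contrast goes from .345/.436/.650 to .476/.540/.722.

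**4. Larger effects.** At ρ=.7 the gain from step 2 falls from .760 − .691 = 6.9 points at d=.5 to 3.8 at d=.67 and 1.7 at d=.77. At ρ=.3 it stays between 15 and 19 points.

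**5. The covariate rule.** Six independent factors each tested at .05: 1 − .95⁶ = 26.5% chance that at least one differs. Simulation (8,000 trials per setting, final-visit change, six candidates, two of them correlated r with change, entered so that they can affect change):

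| ρ | r | no covariates | trigger p<.05 | trigger p<.10 |
|---|---|---|---|---|
| .5 | 0 | .474 | .463 | .454 |
| .5 | .2 | .482 | .472 | .467 |
| .5 | .4 | .468 | .460 | .461 |
| .7 | 0 | .683 | .673 | .668 |
| .7 | .2 | .693 | .686 | .680 |
| .7 | .4 | .681 | .682 | .684 |

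Power moves by −2.0 to +0.3 points; type I error is .038 to .054. For r of 0 to .2, triggered adjustment and no adjustment disagree on significance in 1–2% of null trials and 3–6% at d=.5. Taking the most favourable of the three analyses raises type I error to .056–.062.

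**6. Form of entry.** In a complete three-wave data set, a covariate main effect left the treatment x time estimate and its variance (.01667) unchanged. Only a covariate x time term moved them (variance .01726).

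**The case against.** The planned test is sound. A free-baseline longitudinal model is unbiased under randomisation, and its contrast removes any observed pre-treatment difference. A reader might infer that the pre-treatment score is ignored, or that the planned estimate is biased. Neither follows: the score is in the model as the time-0 outcome. That stands, and it limits this point to precision.

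A reader might also infer that the imbalance rule inflates type I error. Applied mechanically it does not, and its effect on power is at most about 2 points. That stands too, which is why the rule is secondary here.

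The adjustment has a condition. The recruitment text puts the questionnaires before the first session, and the randomisation text keeps assignment from the person taking consent until consent is signed. Neither says whether the questionnaires come before the envelope is opened. If knowing the assignment shifted pre-treatment scores by a lasting .2 SD, the change analysis would be unbiased, while ANCOVA would be off by .2(1−ρ), that is .06 SD at ρ=.7 and .14 SD at ρ=.3. This stands, so the fix must settle the order.

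Finally, the limitations section says the findings will not be definitive, and the plan stresses effect sizes and confidence intervals. This lowers the stakes of any one p-value, but a standard error 8–19% smaller narrows those intervals as well.

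**Conclusion.** The point holds as an efficiency improvement that needs no new data. With 30 per arm and d=.5, baseline adjustment adds about 15, 12 and 7 power points at ρ = .3, .5 and .7. The size depends on ρ, which the documents do not give, and on the effect size: at ρ=.7 the gain is about 4 points at d=.67 and 2 at d=.77. It assumes that pre-treatment scores are not influenced by knowledge of assignment.

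The covariate rule should go because it is undefined and data-driven and brings essentially no power. The documents do not support calling the planned test invalid, or the rule, applied as written, a source of false positives. The remaining risk is discretion over the model, and that is modest.

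**What to change.** In Quantitative Data Analyses (Aim 3), state one primary model that applies whatever the observed balance. Do one of the following, not both:
- remove the arm effect on initial status and keep the planned time contrast (constrained baseline); or
- model the post-baseline scores with the pre-treatment score as covariate (ANCOVA).

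Delete both conditional covariate statements. Either say that no other covariates are used, or name a short fixed list of pre-treatment values entered as covariate x time. Describe baseline characteristics without testing them.

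State that pre-treatment questionnaires are completed before the assignment envelope is opened. If that order cannot be confirmed, keep the free-baseline model as a sensitivity analysis.

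The cost is a revised model statement and its code. If optional extra covariates prove not to be prognostic, expect to lose about 1 to 2 power points: a fixed pair with r=0 took power from .474 to .464 at ρ=.5 and from .683 to .672 at ρ=.7.

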Client Satisfaction Questionnaire-8 (CSQ-8): The CSQ-8 evaluates patients' satisfaction with the service they received (i.e., RISE or the information/referral), with items including "How satisfied are you with the amount of help you have received?" and "If you were to seek help again, would you come back to our program?" (post-treatment and 1 month follow-up only).

Depression Anxiety Stress Scale (DASS) (DASS-Anxiety Subscale): The anxiety subscale contains 14 items which assess autonomic, skeletal muscle effects, situational anxiety, and subjective experiences of anxious affect. 4-point severity/frequency scales are used and summed. The DASS has been shown to have high internal consistency and yield meaningful discriminations in a variety of settings (Lovibond & Lovibond, 1995).

Coping Strategy Inventory- Short Form (CSI-SF) : The CSI-SF was structured to reflect the original CSI scale, with four 4- item subscales: (a) Problem-Focused Engagement, (b) Problem-Focused Disengagement, (c) Emotion-Focused Engagement, and (d) Emotion-Focused Disengagement. Respondents were asked to rate the general frequency with which they utilize each listed coping strategy on the survey and to indicate their choices in the following manner: 1 = "Never", 2 = "Seldom", 3 = "Sometimes", 4 = "Often" and 5 = "Almost Always". Individuals receive scores for each first-tier subscale (Engagement vs. Disengagement: range = 8 – 40), as well as for each of the four second tier subscales (Problem-Focused Engagement, Problem-Focused Disengagement, Emotion-Focused Engagement, and Emotion-Focused Disengagement: range = 4 – 20). Each of the four 2nd tier subscales created contained four items each. The CSI-SF demonstrates reliability and validity.

Acceptability: Brief qualitative and semi-structured interview questions assess patients' perceptions of the feasibility and acceptability of their respective intervention (post-treatment and 1-month follow-up only).

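### Do the CSQ-8 mark at baseline and the missing General Self-efficacy Scale row in Table 4 call for a change to the plan?

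*Combined protocol and SAP*

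**What the plan says.** Under Female VHA Patient Assessments the plan sets three assessments: "We will administer a full battery of psychosocial assessment at pre-treatment, post-treatment assessment (i.e., 10-weeks post enrollment), and 1 month follow-up". The battery is the one described under Measures. The RISE arm has something extra at each session: "Participants in the RISE condition will also complete four brief measures of empowerment, self-efficacy, patient activation and valued action". The section then points to the schedule: "A timeline of all measures is available below in Table 4".

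Table 4 gives the CSQ-8 an X in all three columns (Pre, 10-week, 14-week). The Measures section explains what the form is for, "The CSQ-8 evaluates patients' satisfaction with the service they received", and limits it to "post-treatment and 1 month follow-up only". The description of the enrolment visit fixes the order of events: "Patients will complete the pre-treatment assessment questionnaires (described below), after which patients will receive their randomly assigned 60-minute intervention session".

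The General Self-efficacy Scale appears under Measures, between the Personal Progress Scale and the PAM-13, as "A reliable and valid 10-item scale that is designed to assess optimistic self-beliefs to cope with a variety of difficult demands in life". In Table 4, as read, the Personal Progress Scale row is followed directly by the PAM-13 row. The Phase 3 aims name self-efficacy among the outcomes of Aim 3.

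**The concern.** A schedule that claims to cover every measure is what site staff tend to work from, so its errors can become errors in the data.

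- **CSQ-8.** The table and the Measures text cannot both be right. At the baseline assessment no woman has yet had a RISE or information/referral session, so a satisfaction form given then has nothing to measure.
- **Self-efficacy.** If the scale were really left out of the scheduled battery, its only values would come from RISE sessions. The information/referral arm would have none, and neither arm would have scheduled 10-week or 14-week values. The treatment-by-time comparison in Quantitative Data Analyses (Aim 3) could not be made for an outcome that the aim names.

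The second possibility would matter. The question is whether the plan, read as a whole, leads there.

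**Working it through.** No sample size, power or error-rate figure is involved. The check compares Table 4 with the measure descriptions row by row and then traces what each mismatch would do to the analysis.

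**1. Coverage of the table.** Table 4 as read has 18 rows: 15 with three X's, 1 with two (Acceptability) and 2 with Pre only (fixed demographics, IPV-related head injury); 15 + 1 + 2 = 18. Demographics takes two rows, so 17 distinct measures are covered. The Measures section describes 20 patient measures, and 20 − 17 = 3 have no row: the General Self-efficacy Scale, military sexual trauma and combat exposure. The text gives no time point for the last two, so the table contradicts nothing there.

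**2. Is the CSQ-8 mark real?** Three measures have their timing stated in the Measures text.

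| Measure | Timing in text | Table 4 | Agree? |
|---|---|---|---|
| Demographics | part baseline only, part all three | same split | yes |
| Acceptability interview | post-treatment and follow-up | blank at Pre | yes |
| CSQ-8 | post-treatment and follow-up | X at all three | no |

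Blank cells survive in the Acceptability, fixed demographics and head-injury rows. A misread CSQ-8 cell is therefore unlikely, and the mismatch is in the document.

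**3. What the CSQ-8 slip costs.** At the enrolment target of 68, the table implies 68 × 3 = 204 forms and the text 68 × 2 = 136. The difference is 204 − 136 = 68 forms at most. The one stated use of the CSQ-8, in Quantitative Data Analyses (Aim 3), is to examine the acceptability of both interventions. No change from baseline is specified for it. The post-treatment and follow-up scores are the same whether or not a baseline form exists.

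**4. What the text says about self-efficacy.** Four points support three-point collection in both arms:

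- The full battery described under Measures is given at all three assessments, and the scale is listed there.
- The RISE session measures are described as additional to that battery.
- Aim 3 names self-efficacy as an outcome, and the outcome model codes time as 0, 1 and 2 for the three assessments.
- The measures for the other three session constructs (Personal Progress Scale, PAM-13, VLQ) each have a row with three X's.

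One argument should carry no weight: that the scale is listed without a time limit. The head-injury screener is also listed without one, yet Table 4 gives it at Pre only. For the same reason, the full battery cannot mean literally every measure at every visit. The support comes from the four points together; no sentence gives the timing of this scale by name.

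**5. What would have to happen for data to be lost.** Staff would have to follow the table and disregard the assessment paragraph that introduces it. Nothing in the document shows that this happened or will happen. The number of affected assessments could lie anywhere from none to all, and the document gives no basis for choosing a value, so none is claimed.

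**The case for a change.** The best case for a change is that correction is almost free and the downside is not trivial. The CSQ-8 entry is a plain contradiction, and the text shows which side is coherent. Self-efficacy is a named outcome and one of the three constructs through which the RISE conceptual model expects the intervention to work. Losing it in the comparison arm could not be repaired afterwards. The table is presented as complete, so staff might reasonably rely on it.

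Part of this stands. The CSQ-8 mark conflicts with the Measures text, and removing it is the sensible reading. It is also reasonable for the team to look at the source table and see whether a self-efficacy row is there.

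The rest does not carry the weight. The cheapness of a correction does not show that a result depends on it, and none does for the CSQ-8. For self-efficacy, the missing row is an omission and not a contrary instruction. Rows can be lost when a table is extracted from a PDF, and the gap lies next to the one measure row that is bold throughout, where the formatting is irregular. Even if the row is truly absent, the surrounding text fills the gap in the way any analyst would expect.

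**Conclusion.** The textual mismatch is real but minor, and the plan does not need to change.

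- **CSQ-8:** a clerical slip, worth at most 68 superfluous baseline forms at full enrolment. It has no effect on the acceptability analysis or on any estimate, power figure or conclusion.
- **General Self-efficacy Scale:** a query about the source table, held with less confidence than the CSQ-8 point. Followed as written, the text yields the scale at three assessments in both arms, which is what the outcome model needs.

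This rests on two assumptions: that staff follow the assessment and Measures text where the table is silent or at odds with it, and that no undocumented analysis uses a baseline CSQ-8 score. If the team found that self-efficacy had been collected only at RISE sessions, the second point would become a substantive one. The document gives no sign of that.
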